Disease-focused clinical teams, e.g., breast, colorectal, etc. will comprise the clusters. All clusters will include both medical oncologists and mid-level providers.

Allocation. There will be 5 sequences in our design, with 3 clusters randomized to initiate the intervention for each sequence. Pre-E2C2 baseline assessment will occur for all clusters starting 7 months prior to the first sequence. Each sequence will occur 8 months apart; data collected prior to the intervention will provide a within-site control group for each site. The allocation is illustrated in **Figure 1**. To ensure balanced cluster characteristics we will stratify randomization based on cluster size and site.

Figure 1. Final allocation of 15 cancer care sites to 5 sequences over 6 time periods.

| Cluster | Strata | Step | | | | | | Sequence |
|--------------|--------|------|---|---|---|---|---|----------|
| | | 1 | 2 | 3 | 4 | 5 | 6 | |
| SWWI | 2 | 0 | 1 | 1 | 1 | 1 | 1 | |
| Rochester 1 | 1 | 0 | 1 | 1 | 1 | 1 | 1 | 011111 |
| Rochester 2 | 4 | 0 | 1 | 1 | 1 | 1 | 1 | |
| Rochester 3 | 2 | 0 | 0 | 1 | 1 | 1 | 1 | |
| Rochester 4 | 1 | 0 | 0 | 1 | 1 | 1 | 1 | 001111 |
| Rochester 5 | 4 | 0 | 0 | 1 | 1 | 1 | 1 | |
| Rochester 6 | 2 | 0 | 0 | 0 | 1 | 1 | 1 | |
| NWWI | 3 | 0 | 0 | 0 | 1 | 1 | 1 | 000111 |
| Rochester 7 | 1 | 0 | 0 | 0 | 1 | 1 | 1 | |
| SWMN | 3 | 0 | 0 | 0 | 0 | 1 | 1 | |
| Rochester 8 | 4 | 0 | 0 | 0 | 0 | 1 | 1 | 000011 |
| Rochester 9 | 1 | 0 | 0 | 0 | 0 | 1 | 1 | |
| Rochester 10 | 1 | 0 | 0 | 0 | 0 | 0 | 1 | |
| Rochester 11 | 1 | 0 | 0 | 0 | 0 | 0 | 1 | 000001 |
| SEMN | 2 | 0 | 0 | 0 | 0 | 0 | 1 | |

| | | | | | | |
|--|--|--|--|--|--|--|
| | | | | | | |
| | | | | | | |

Control condition

Intervention condition

T1 6 months

T2-T6 8 months

Interventions

The E2C2 intervention will include patient- and clinician-directed elements that are designed to increase the frequency with which patients receive individualized, preference-concordant, and guideline-based care for their symptoms and to increase rates of symptom control.

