A version of the statistical model above was fit to 79 weeks of preliminary baseline data (i.e., with no intervention effect X_{kt}) in order to estimate the parameters (e.g., $\boldsymbol{\nu}_A, \boldsymbol{\Sigma}_A$) needed to simulate longitudinal data for the 15 clusters. Clusters were randomly allocated to the steps in **Figure 1**, and treatment effects due to intervention were generated on a grid of eight values $\nu_{1B} = 0.00, 0.01, 0.02, 0.03, 0.05, 0.10, 0.15, 0.20$, with the remaining $\nu_{2B} = \nu_{3B} = \nu_{4B} = \nu_{5B} = 0$ to assume the most conservative case (i.e., only a single symptom is affected by the intervention). The cluster effects were then generated according to $\boldsymbol{B}_k \sim N(\boldsymbol{\nu}_B, \sqrt{\nu_{1B}} \boldsymbol{\Sigma}_A)$. This data generation process was used to simulate 100 data sets under each of the eight grid values for ν_{1B} . The full model above was then used to estimate $\boldsymbol{\nu}_B$ and test the hypothesis that all $\nu_{jB} = 0$, via simultaneous credible bounds.⁹⁷ The results are provided in **Figure 3**. As can be seen in the figure, the test keeps very close to the nominal level (i.e., 0.01, 0.05, or 0.10, respectively) when there is no effect. However, the power rises quickly to detect even a small average score difference of even 0.10 with 70% power (at 0.05 LOS) and a difference of 0.20 with nearly 100% power.

Data Analysis Plan:

Specific Aim 1 Analyses.

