To test the primary hypothesis H1a for our primary outcomes, we will use generalized linear mixed models to assess the effects of the intervention on each of the 6 SPPADE scores⁹⁰. All models will account for correlation of outcomes within clusters and across patients, and for changes in this correlation over time. We will adjust for time, measured by study period, to account for temporal effects. Each score will be adjusted for the prior score, with a coefficient that depends on the time t since the prior score; to account for potential changes in correlation of outcomes by over time we will include autoregressive terms at the patient level.⁹¹ To account for changing correlation within clusters over time we will incorporate a discrete-time correlation structure.⁹⁸

Our primary analysis will treat each SPPADE score as a continuous variable and employ a mixed effects generalized multivariate model; we will model all 6 scores jointly, which will allow us to account for the correlation between them and avoid correcting for multiple hypothesis tests.

Specifically, let Y_{ijkm} be the i^{th} score ($i=1,\dots,6$) of the j^{th} encounter for the k^{th} patient in the m^{th} cluster ($m=1,\dots,15$), for $j = 2,\dots$; the first score for each patient ($j=1$) is a baseline score collected during the first visit, not an outcome. Let $w=1,\dots,6$ indicate the trial step during which the survey is collected.

Then to test the hypothesis that the intervention impacts the 6 symptom scores we will estimate the joint models:

$$Y_{ijkm} = A_{ikm} + \mathbf{B}_i X_{jkm} + \mathbf{L}_i(t) Y_{i[j-1]km} + \mathbf{F} \mathbf{Z}_k + \mathbf{D} \mathbf{S}_m + \mathbf{Q} q_{jmk} + \mu_{imw} + \nu_{it} \quad ; \quad i=1,\dots,6 \quad (1)$$

where

X_{jkm} is an intervention indicator which equals 1 if encounter j for patient k in cluster m was post intervention and 0 otherwise;

\mathbf{B}_i is a vector of fixed effects for the intervention on symptom score i , $i = 1,\dots,6$;

\mathbf{L}_i is a vector of time dependent lags, representing the effect of the most recent measurement on the current one, as a function of time t in days between measures;

\mathbf{Z}_k is a vector of patient factors for patient k , \mathbf{F} is a corresponding vector of fixed effects;

\mathbf{S}_m is a cluster level set of indicators for randomization strata, \mathbf{D} is a vector of fixed effects;

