\mathbf{Q} is a vector representing the secular time effect, where q_{jmk} is the calendar quarter; and, the time elapsed since encounter $j-1$; for $j=2,\dots$

In addition

A_{ikm} is a vector of random effects, $[A_{1km},\dots,A_{5km}]$ specified as varying across patients nested within clusters

$$A_{ikm} \sim [A_i + \alpha_{ikm} + \gamma_{im}]; \quad i=1,\dots,6$$

$$[\alpha_{ikm}] \sim N(0, \Sigma_\alpha)$$

$$[\gamma_{im}] \sim N(0, \Sigma_\gamma)$$

where Σ s are exchangeable correlation matrices.

μ_{imw} , $i=1,\dots,6$ is a discrete-time vector of random effects for each cluster m and step w ; and,

ν_{it} , $i=1,\dots,6$ is a multivariate autoregressive process of order 1, AR(1) with Gaussian noise, to account for time dependent correlation of responses within each patient over time; and,

Prior to estimating this model, the distributions of the SPPADE scores will be examined and, if appropriate, transformed to have approximately normal distributions. Covariates will be similarly reviewed and either transformed or categorized before inclusion in the model.

In general, fitting the above models (1) which has several random effects (in both time and across clusters) can be challenging. However, Markov Chain Monte Carlo estimation is very effective at fitting such models and are appropriate for assessing stepped-wedge cluster randomized designs.⁹⁹ Moreover, by incorporating historical time trends into our priors for the effect of calendar time, a Bayesian model can increase statistical power relative to a frequentist approach.¹⁰⁰ All other priors will be flat. In the event that model (1) can't be estimated, we will simplify the error structure and other features using review of variable distributions and correlations, including intra-cluster correlations and time dependent correlation, to inform the simplifications. Then, using our final model we will calculate posterior probabilities and credible intervals to assess whether coefficients differ from zero; specifically, we will achieve the primary aim of the study by calculating the posterior probabilities that each of B_1, \dots, B_6 is greater than 0; we will accept that the intervention is effective if $PP[\text{abs}(B_i) > 0, i=1,\dots,6] \geq 0.80$.

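### The only informative prior in the primary model sits on calendar time, its source, mean and SD are unstated, and no refit shows how far the intervention effects depend on it

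*Combined protocol and SAP*

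**What the plan says.** The estimation paragraph under Hypotheses H1a (Data Analysis Plan, Specific Aim 1) chooses MCMC and gives as one reason that "by incorporating historical time trends into our priors for the effect of calendar time, a Bayesian model can increase statistical power" compared with a frequentist analysis. The next sentence reads "All other priors will be flat". Taken together, these plan an informative prior for calendar time and for nothing else. The text gives no data source, centre, spread or down-weighting rule for it, and no check for conflict between prior and data.

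The time term itself is described in two ways. The text introducing the H1a models says "We will adjust for time, measured by study period, to account for temporal effects", while the definitions under model (1) say that Q "is a vector representing the secular time effect, where q_{jmk} is the calendar quarter". So it is also unclear which parameters carry the prior.

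The design is set out under Allocation: "There will be 5 sequences in our design, with 3 clusters randomized to initiate the intervention for each sequence", with six steps in Figure 1. The same H1a section keeps a cluster-period model with step indicators in reserve in case the survey-level model cannot be computed. The Power Statement mentions "79 weeks of preliminary baseline data" as the basis for the power simulation.

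**The concern.** Calendar time is the nuisance most closely tied to exposure in this design. In Figure 1 the share of clusters under intervention goes 0/15, 3/15, 6/15, 9/15, 12/15, 15/15 over the six steps. With flat priors on step effects, a trend common to all clusters is removed from B_i completely. With an informative prior the model partly trusts history. If symptoms, treatments or the mix of responders move differently during the trial, some of the difference is credited to the intervention while its interval narrows. The extra precision and the exposure to bias come from the same source.

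Without a stated prior, and without a fit that leaves it out, a reader cannot tell how much of a finding on B_i comes from the trial's own data.

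**Working it through.** **1. The plan's power figure and the SE it implies.** The Power Statement gives 70% power at the 0.05 level for a 0.10-point difference, and nearly 100% for 0.20. The simulation cannot be re-run because its fitted parameters are not printed, but its implied SE follows:

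- SE = 0.10 / (1.960 + 0.524) = 0.0403. At 0.20, power = Φ(0.20/0.0403 − 1.960) = 99.9%, which agrees with the plan.
- The plan tests through simultaneous bounds. A Bonferroni value for five effects gives 0.10 / (2.576 + 0.524) = 0.032, also nearly 100% at 0.20.

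The plan does not say whether the informative prior was used in that simulation. I take 0.0403 as the flat-prior SE, as an assumption.

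**2. Simplified model.** The data are 15 × 6 cluster-step means laid out as in Figure 1 ("Final allocation of 15 cancer care sites to 5 sequences over 6 time periods"), with a random cluster effect (variance ratio to residual of 1 or 3) and residual variance scaled so that the flat-prior SE of B is 0.0403. The five step-to-step changes have independent normal priors centred on the historical trend with SD τ. The true trend departs from history by d points at every step, and the true effect is zero.

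Write A = X′V⁻¹X, P for the prior precision (1/τ² on the step changes, 0 elsewhere) and M = (A + P)⁻¹. Then:

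- bias b = the B element of M·A·θ, where θ holds d for each step change;
- posterior SE = √M_BB;
- sampling SD s = √(M·A·M)_BB;
- chance that a 95% interval excludes zero = Φ((b − 1.960·SE)/s) + Φ((−b − 1.960·SE)/s);
- chance that the posterior probability in the drift direction reaches 0.80 = Φ((b − 0.842·SE)/s).

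One line in full (d = 0.02, τ = 0.01, ratio 1): b = 0.0486, SE = 0.0289, s = 0.0267. The first exclusion term is Φ((0.0486 − 0.0566)/0.0267) = Φ(−0.30) = 0.38, and the second is negligible. The directional figure is Φ((0.0486 − 0.0243)/0.0267) = Φ(0.91) = 0.82.

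**3. Results, no true effect.**

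| Departure per step (total by step 6) | Prior SD per step | Bias in B | Posterior SE | 95% interval excludes 0 |
|---|---|---|---|---|
| 0.02 (5 × 0.02 = 0.10) | 0.01 | 0.05 | 0.029 | 38–40% |
| | 0.02 | 0.03 | 0.033 | 14% |
| | 0.04 | 0.015 | 0.037 | 5% |
| 0.04 (5 × 0.04 = 0.20) | 0.01 | 0.10 | 0.029 | 94–95% |
| | 0.02 | 0.07 | 0.033 | 53% |
| | 0.04 | 0.03 | 0.037 | 11% |
| | 0.08 | 0.009 | 0.039 | 5% |
| either | flat | 0 | 0.040 | 5% |

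At 0.02 per step the directional posterior probability reaches 0.80 in about 82%, 58% and 32% of trials for τ = 0.01, 0.02 and 0.04, against 20% with a flat prior.

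**4. What the prior buys.** Approximate power at 0.10 is Φ(0.10/SE − 1.960). For SE 0.029, 0.033, 0.0372 and 0.0394 (τ = 0.01, 0.02, 0.04, 0.08) this gives about 93%, 86%, 77% and 72%, against 70% with a flat prior. At τ = 0.08 the SE falls by only about 2% (0.0394 against 0.0403).

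**5. Sensitivity.** With a flat-prior SE of 0.032, d = 0.02 gives a bias of about 0.045, 0.027 and 0.010, and exclusion in about 46–48%, 14% and 5%. A second version places the prior on each step's level instead of on the changes. There, a prior SD of 0.10 lifts power from 70% to 80% and passes about 21% of a linear departure into B.

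**The case against.** Several points on the other side stand.

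- **The size is assumed.** No document gives a drift or a prior SD. The 94–95% row needs a miss of four prior SDs, in the same direction, at all five steps. Where the miss equals one prior SD per step, the interval excludes zero in only about 11–14% of trials (11% at 0.01, 14% at 0.02, 11% at 0.04).
- **The model is simpler than the plan's.** It uses step changes where model (1) is written with calendar quarter. It also leaves out the adjustment for each patient's previous score, which may absorb part of a lasting drift.
- **Some cover exists.** The cluster-period model has step indicators and no stated historical prior. But it becomes primary only if the survey-level model fails, its comparison is meant to test the use of the cluster-period approach, and it changes the unit of analysis at the same time. It cannot isolate the time prior.

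A reader might also infer three things that the documents do not support. First, that the 79 weeks is the source of the prior and too short for a trial of 46 to 47 months (6 or 7 + 5 × 8): those data are named only for the power simulation. Second, that H1b is biased in the same way: it tests the interaction D_i, where a time shift common to elevated and non-elevated scores would largely cancel, and no bias in D_i has been shown. Third, that effectiveness may be claimed only if the flat-prior fit also succeeds: that would undo the power gain the sponsor chose, and it is a trade-off, not a correction.

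**Conclusion.** The point holds as a gap in transparency and sensitivity analysis for model (1). The plan commits to an informative calendar-time prior, leaves it unspecified, and provides nothing that shows how much B_i rests on it. If the prior is tight enough to deliver the power gain cited, a modest departure of 0.02 per step could bias B by roughly 0.015 to 0.05 points, up to half of the 0.10-point difference used for power. At 0.04 per step the range is about 0.03 to 0.10. If the prior is loose (SD 0.08 or more per step), the problem is negligible, and so is the benefit.

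These figures rest on the assumed SE, drift, prior SD and simplified model. The bias can inflate or hide a benefit, depending on whether the trial-period trend is better or worse than history. It would be wrong to conclude that the primary result will be biased, or that false claims at the 95% level are to be expected: the documents contain nothing that fixes the prior SD or the drift.

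**What to change.** 1. Before analysis, state the source, mean and SD of the calendar-time prior. Settle whether the time term is calendar quarter or study period.
2. Prespecify one sensitivity refit of model (1), or of whichever simplified version becomes final, identical except for flat priors on the calendar-time effects.
3. Report B_i from both fits side by side, with the prior and posterior of the time effects. Say in the conclusion if the finding of effectiveness depends on the informative prior.
4. Make any comparison with the 0.80 threshold on a directional probability. As printed, the rule asks for the probability that abs(B_i) exceeds 0, which is 1 for any continuous posterior, so every fit would pass.

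The refit need not be a second condition for success, and a refit of model (2) is optional.

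Cost: one further MCMC run of a model that the plan itself expects to be hard to fit, and possibly a wider interval printed beside the primary one.

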In the event that the model with patient surveys as the unit of analysis cannot be computed, we will use an alternative cluster-period model for the primary analysis. We will aggregate outcomes and covariates for each cluster for each time period and use these cluster-level estimates to assess the effect of the intervention. We will calculate the mean of each of the 6 different SPPADE NRS scores collected during trial cluster-periods. We will also calculate the mean baseline score for each participant that reports one or more ePROMs. We will then test the first primary hypothesis using a multivariate regression model using these 15 clusters \times 6 period = 90 cluster-period values, including an indicator for intervention status for each cluster-period, and adjusting for mean baseline scores and including indicators for study step to account for secular trends and for indicators for cluster to account for cancer type. We will adjust for cluster-period averaged values of factors of patients reporting during each period for which the SMD between intervention and control cluster-periods are >0.2 .

To assess the robustness of using the CP model, we will replicate the main analyses for each symptom NRS score. We will use the originally specified generalized mixed effects model, as well as the CP model adapted to the univariate dependent variable. This former model will be estimated at the survey level, with random effects for surveys within patients and patients within clusters; these 6 models (one for each symptom score) also included all pre-specified patient covariates, baseline symptom score, the lag in weeks since the baseline measurement and the interaction of the lag time with the baseline effect.

Because there is potential for the intervention to impact the baseline scores as well, we will replicate the cluster-period and survey level models each symptom score, including patients with only 1 survey score.

We will estimate models using the STAN software package.

Hypotheses H1b

To test whether the intervention has a differential effect on those patients with at least one elevated symptom score,

we will construct an indicator, E_{ijkm} , varying by measurement time, which indicates whether the i^{th} prior symptom score was elevated (>3). By interacting these indicators with the main intervention effects B_i we can assess the impact of the intervention on the corresponding scores of patients with at least one elevated score:

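### The survey-level models that check the cluster-period analysis list no cluster-by-step effect, and nothing protects that effect if the primary model has to be simplified

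*Combined protocol and SAP*

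**What the plan says.** All of this is in the Data Analysis Plan, Specific Aim 1, Hypotheses H1a.

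- **General requirement.** All models are to allow for correlation within clusters and across patients, and for change in that correlation over time: "To account for changing correlation within clusters over time we will incorporate a discrete-time correlation structure".
- **Model (1), the primary model.** It is a joint model of the six scores. It has patient and cluster random effects, a patient-level AR(1) process, and a term that "is a discrete-time vector of random effects for each cluster m and step w".
- **If model (1) cannot be estimated.** The plan states: "we will simplify the error structure and other features using review of variable distributions and correlations". The correlations to be looked at are those inside clusters and those across time. The plan does not list which terms may go or which must stay. The decision rule is then applied to whatever model is final.
- **Second fallback.** If the survey-level model cannot be computed, a cluster-period model on 15 x 6 = 90 values becomes primary, with indicators for cluster and step.
- **Check on the second fallback.** "To assess the robustness of using the CP model, we will replicate the main analyses for each symptom NRS score". For this, "We will use the originally specified generalized mixed effects model, as well as the CP model adapted to the univariate dependent variable". The survey-level version is then described as six univariate models "with random effects for surveys within patients and patients within clusters". The survey-level models are used again in the analysis that adds patients with only one survey.

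**The concern.** In a stepped wedge trial, treatment status is a property of a cluster in a step. If a cluster's mean score drifts from one step to the next for reasons of its own (staffing, case mix, other changes in care), that drift looks like a treatment effect. The only protection is a variance component at that level. Model (1) has one; the random effects listed for the survey-level check do not include one. A random intercept per cluster removes only the stable difference between clusters, and a patient random effect does not absorb a shift shared by all patients of a cluster in one step.

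The check is meant to show whether the cluster-period result can be trusted. Fitted as listed, it would look more precise than it is, so its agreement could give false reassurance and its disagreement could mislead. Model (1) is exposed to the same loss if it has to be simplified, because the text keeps no term in place.

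**Working it through.** **1. The plan's own figure.** The Power Statement reports near-nominal error for the full model, 70% power at a difference of 0.10 and nearly 100% at 0.20 (0.05 level). It cannot be rebuilt, because the variance parameters and cluster sizes are not given. The two power points do agree with each other. For a two-sided test, SE = 0.10/(1.960 + 0.524) = 0.0403, and power at 0.20 = Φ(0.20/0.0403 − 1.960) = Φ(3.00) = 0.999. With 100 simulated data sets, an observed 5% error has a 95% interval of 1.6-11.3%. The figure describes the full model, so it says nothing about a model without the cluster-by-step effect.

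**2. Inputs.** From Figure 1: 15 clusters, 5 sequences of 3, 6 steps. Assumed, because undocumented: total variance 1; intracluster correlation ρ = 0.01-0.05; cluster autocorrelation CAC = 0.95-0.80; n = 100 or 500 surveys per cluster-period. The only volume figure, under Cancer Patient Enrollment, is about 2,500 new diagnoses a year. That gives 2,500/15 x 6/12 = 83 to 2,500/15 x 8/12 = 111 new patients per cluster-period. Follow-up patients and repeat visits add to this; non-response reduces it. Patient-level correlation is not modelled, so n is best read as an effective number of independent surveys.

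**3. Formula.** Between steps, a cluster-period mean varies around its cluster's level with variance (1−ρ)/n + ρ(1−CAC). Without the cluster-by-step effect the model sees only (1−ρ)/n. To a close approximation, the true variance of the treatment estimate exceeds the reported one by the ratio

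VR = 1 + nρ(1−CAC)/(1−ρ).

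The false-positive rate at nominal two-sided 5% is 2[1 − Φ(1.96/√VR)]. Example: n = 500, ρ = 0.05, CAC = 0.80 gives VR = 1 + 500 x 0.05 x 0.20/0.95 = 6.26, and 2[1 − Φ(1.96/2.50)] = 0.43.

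**4. Results.** The GLS columns use generalised least squares on the actual 15 x 6 design with step effects. The REML columns are simulations with 1,000 replicates per row.

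| n | ρ | CAC | VR (formula) | GLS, term omitted | REML, term omitted | REML, term kept | GLS, one-sided nominal 20%, term omitted |
|---|---|---|---|---|---|---|---|
| 100 | 0.01 | 0.95 | 1.05 | 5.5% | 4.7% | 4.0% | 20.5% |
| 100 | 0.02 | 0.90 | 1.20 | 7.3% | 6.8% | 5.1% | 22.0% |
| 100 | 0.05 | 0.80 | 2.05 | 16.6% | 18.5% | 4.3% | 27.6% |
| 500 | 0.01 | 0.95 | 1.25 | 7.9% | 8.3% | 4.9% | 22.5% |
| 500 | 0.02 | 0.90 | 2.02 | 16.6% | 17.5% | 5.3% | 27.6% |
| 500 | 0.05 | 0.80 | 6.26 | 43.0% | 44.5% | 6.0% | 36.7% |

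**5. The plan's decision rule.** The rule is a posterior probability of at least 0.80, not a 5% test. As printed it concerns the absolute value of a continuous coefficient exceeding zero, which always has probability 1, so a reading has to be chosen.

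- *One coefficient, flat prior.* The nominal rate is 20%, and without the term it is 1 − Φ(0.842/√VR), the last column. As VR grows this tends to 50%, so the rise cannot exceed 2.5-fold.
- *All six coefficients beneficial together* (between-score correlation assumed 0.5). The rate goes from 0.5% to 1.9% at VR = 2 and 5.8% at VR = 6: a large ratio from a very low base.

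**6. The cluster-period fallback.** It was simulated as least squares on the 90 values with cluster and step indicators (69 df), without the baseline covariate. Its error stayed at 4.5-5.1%, including when within-cluster correlation decays over time. It works at the level at which treatment varies.

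**The case against.** Four points deserve weight.

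- **The list may be shorthand.** The same sentence names no intervention indicator and no secular trend either, and the general requirement covers all models. But the sentence is not simply model (1) abbreviated: it also replaces the prior score with the baseline score and a lag since baseline. A programmer could reasonably fit what is listed. At the least, the section contradicts itself.
- **These are robustness models.** This stands. A reader might infer that the primary analysis will be run without the cluster-by-step effect, so that the trial's false-positive rate rises severalfold. The documents do not support that. Model (1) includes the term, simplification happens only if model (1) cannot be estimated, the text does not say this term would go, and the one fully specified fallback holds its error rate.
- **The size rests on assumptions.** This stands too. At 100 surveys per cluster-period with ρ of 0.01-0.02 and CAC of 0.90 or more, the rate is only about 5-7%. The stated power does not settle the matter: the Power Statement also simulated intervention effects that differ between clusters, so the implied SE of 0.040 cannot be assigned to cluster-by-step variation.
- **The review of correlations is not a review of results.** A reader might infer that the error structure will be picked to suit the treatment effect. The text speaks of distributions and correlations, and a review of correlations should reveal a large cluster-by-step component. What is missing is a statement that the term stays.

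**Conclusion.** The concern holds for the survey-level robustness models. As listed they omit a term that model (1) contains and the plan's general requirement calls for, and fitted that way they give intervals that are too narrow. At nominal 5% the false-positive rate is about 6-17% at 100 and 8-43% at 500 surveys per cluster-period, for ρ of 0.01-0.05 and CAC of 0.95-0.80, all assumed. On a one-coefficient reading of the 0.80 rule the rise is smaller: from 20% to about 37% in the worst row, with a ceiling of 50%. The direction is certain whenever there is any cluster-by-step variation; the size is not documented. For the primary analysis the finding is conditional: a simplified model (1) could lose the same term, because nothing prevents it, but the plan does not say that it will.

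**What to change.** 1. Add the cluster-by-step random effect to the six survey-level models that check the cluster-period analysis, and to their repeat with single-survey patients.
2. State that any simplified survey-level version of model (1) keeps the cluster and cluster-by-step effects. Simplify the patient-level AR(1) process and the Σ matrices first, and keep the six scores joint. Fitting the scores separately would give up the joint model on which the plan relies to avoid a multiplicity correction.
3. State that if a model with these terms cannot be fitted, the cluster-period model becomes primary.

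This changes wording only: no new data and no change of design. The price is somewhat wider intervals in the survey-level models and one more variance component to fit.
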